6.3 Study Intervention Compliance (How to maintain, evaluate, and verify study compliance)

After each medication, the subject should be required to return to the study center for review, and the compliance of the study can be verified according to the subject's review. During the late follow-up, the study team members must conduct a telephone follow-up communication

with the subject and reasonably arrange the review visit.

6.4 Concomitant therapy (permitted adjuvant medication, complementary / replacement therapy)

If the subject has hypertension, diabetes, coronary heart disease and other diseases that need long-term drug control, the investigator and the relevant specialist should evaluate the impact of the disease and the relevant study protocol and determine the dose and duration of adjuvant medication.

6.4.1 Rescue (drug, treatment methods, relevant records.....)

The life hazards during the implementation of the clinical study protocol should be implemented in accordance with the clinical rescue plan, such as cardiopulmonary resuscitation, emergency airway management, emergency surgical treatment, relevant records during hospitalization should be recorded in the medical record system, after discharge should be recorded in the adverse event record form, and the investigator should analyze whether the rescue causes are related to the study and discuss and discuss synchronously in the rescue records.

7. Discontinuation of the study intervention / subject discontinuation and withdrawal*

7.1 Study Intervention discontinuation (reasons / criteria: such as how many adverse events occurred, length of study discontinuation, how data were collected during discontinuation and how to reactivate the study intervention, whether follow-up was continued during discontinuation)

If the Grade 5 adverse event of CTCAE 5.0 standard reaches 10% of the number of subjects, the study should be discontinued and the drug safety of the study protocol should be discussed to determine whether to adjust the dose of drugs in the study protocol, continue the follow-up during the study suspension, and maintain the follow-up record of the original

subject.

7.2 Subjects discontinuation / withdrawal from the study (possible reason for subject discontinuation; involving implantable device, discuss how to remove / replace, obtain alternative materials, later contact with the subject, etc.)

When the subject stops or withdraws from the study due to dissatisfaction with the treatment effect of the study plan or his own economic reasons, he should actively communicate with the subject, encourage the subject to actively treat and help them apply for public welfare funds to complete the treatment. If the subject clearly withdraws, the investigator can continue to complete the follow-up without the study intervention.

7.3 Loss to follow-up (measures to reduce and reduce missing data due to loss to follow-up)

The investigator should keep the contact information of multiple subjects and the contact information of the family members after the subjects are enrolled. The investigator should actively contact the subjects by phone after leaving the hospital, timely understand the condition and arrange the subject to the hospital in advance for the next stage of treatment.

8. Adverse events and unexpected events

Adverse events (AEs) are adverse medical events occurring after the subject receives the treatment, but they are not necessarily causally related to the treatment. An adverse event can be any adverse and unexpected signs (including abnormal laboratory findings), symptoms, or illness associated to the use of treatment, regardless of relation to treatment. It includes, but is not limited to, :

(1) the exacerbation of the preexisting disease before the use of the study treatment measures;

- (2) The frequency or severity of seizure events increased before the use of study treatment;
- (3) Abnormal changes detected or diagnosed after the use of the study treatment measures, although such abnormal changes may have existed before the treatment;
- (4) deterioration of disease or symptoms that persisted before the study.

Causal relationship between adverse events and treatment measures: In the trial, the investigator should make a comprehensive analysis according to the specific situation of adverse events and the past history, concomitant diseases and concomitant medication to judge the relationship between adverse events and treatment measures. The relationship between adverse events and treatment measures is divided as "definitely related, most likely related, likely related, possibly unrelated and unrelated".

None: Adverse events were not associated with treatment measures.

Probably unrelated: The occurrence of adverse events is more likely related to other factors such as medication or concomitant

Disease, or the timing of the event suggests that it is unlikely to be causally related to treatment measures.

Possible concern: Adverse events may be caused by therapeutic measures. Cannot exclude whether it may be caused by other

Factors, such as: medication conditions or concomitant diseases. The occurrence of adverse events and treatment measures have a reasonable time order, and the causal relationship between events and treatment measures cannot be excluded.

It is likely that: adverse events may be caused by treatment measures. There is a reasonable temporal sequence of event occurrence and treatment measures.

Positive concern: The type of adverse event has been identified as

treatment and no other reason

Explanation, such as: medication status and concomitant diseases. The timing of the event strongly suggests causality.

Event severity criteria can be according to the Common AE evaluation criteria version CTCAE 5.0 (US Department of Health and Human Services).

Beyond the above criteria list, refer to the following criteria:

Mild: Symptoms or signs but tolerable.

Moderate; discomfort enough to interfere with normal life.

Severe: Normal activities are already impossible.

All information about adverse events, whether mentioned by the patient, found by the investigator, or found by physical examination, laboratory examination, etc., should be recorded on the study medical record and case report form. During the trial, the time, duration, symptoms, signs, severity, measures taken, outcome and relationship assessment of adverse events should be carefully observed and recorded, and the results should be appropriately followed up.

Possible adverse events include: medication-related complications; procedure-related complications; and related complications after withdrawal.

The investigator should use medical terms / concepts to record AEs or SAEs. Its type, degree, occurrence time, duration, treatment measures, treatment are recorded in detail. The association of the combination of complications and medication with the study treatment was evaluated. All AEs (including SAEs) should be recorded on the Adverse Event Form for the CRF. Any patient who is treated must be evaluated for toxicity. The occurrence of any adverse events (AEs) should be graded according to the NCI Common AE classification criteria (NCI-CTCAE version 5.0).

9. Data collection and management

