2.2.3 Potential risk and benefit evaluation

Smetinib Insulphate capsule is indicated for pediatric patients with

neurofibromatosis type I (NF 1) aged 3 years and older with symptomatic, inoperable plexiform neurofibromas (PN). It was approved to list in China on April 28, 2023, and was included in the medical insurance directory on December 13, 2023. Several guidelines, consensus and diagnosis and treatment norms in China recommend selmetinib hydrohydrogen sulfate for the treatment of NF 1-PN. The most common toxicity of selmetinib hydrosulphate capsules is grade 1 and 2 gastrointestinal symptoms (nausea, vomiting, or diarrhea), asymptomatic elevated creatine phosphokinase levels, acne-like rash, and paronychia with good safety and tolerability. Therefore, this clinical study protocol has a low risk of disease progression and serious adverse events on the treatment of NF 1^[14, 15]. At the same time, in the future studies, the investigators will pay more attention to the subjects' systemic condition and tumor treatment condition, and the subjects will also gain some clinical benefit in this study.

3. Study objective and endpoint (list presentation objective (specific issues to be addressed), corresponding to the outcome measures)

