5.2 Study design process

5.2.1 Study the specific implementation process

This study started from the recruitment of subjects, with clinical diagnosis, definite diagnosis by pathological biopsy, primary screening according to inclusion criteria and exclusion criteria, and signed informed consent before enrollment. After evaluation as indication for surgical resection and surgical treatment, selmetinib hydrosulphate capsules. PFS, ORR and DOR were assessed after 6 cycles of oral selhydrosulphate capsules (20–50mg bid).

Demographic data	✓										
medical history	✓				✓			✓	✓	✓	✓
ECOG grade	✓	✓	✓	✓	✓	✓	✓	✓	✓	✓	✓
check-up	✓	✓	✓	✓	✓	✓	✓	✓	✓	✓	✓
vital sign	✓	✓	✓	✓	✓	✓	✓	✓	✓	✓	✓
electrocardiogram	✓				✓			✓	✓	✓	✓
routine blood test	✓		✓	✓	✓	✓	✓	✓	✓	✓	✓
Blood biochemical	✓		✓	✓	✓	✓	✓	✓	✓	✓	✓
Liver, kidney, and cardiac function	✓		✓	✓	✓	✓	✓	✓	✓	✓	✓
coagulation function	✓		✓	✓	✓	✓	✓	✓	✓	✓	✓
Heart ultrasound	✓				✓			✓	✓	✓	✓
Pathological biopsy	✓										
Infectious disease examination (hepatitis B, hepatitis C, HIV, syphilis)	✓										
Imaging examination	✓				✓			✓	✓	✓	✓
complication And adverse event assessment			✓	✓	✓	✓	✓	✓	✓	✓	✓

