Main index analysis adopts LOCF (last observation carried forward) method, that is, the main index data is not observed at the last time; the secondary indicators and safety indicators are not filled.

6. Research intervention*

6.1 Study intervention content (description of intervention content, implementation steps, dose and route of intervention drug, frequency of intervention, product of test group and control group, etc.)

All patients received oral selmetinib hydrosulphate capsules (20–50mg bid) daily for 30 days for 6 cycles, based on individualized patient body surface area (BSA).

6.2 Preparation / handling / storage / responsibilities (drug versus control article allocation plan when intervention should be specified)

The use of drugs must be recorded in the patient's medical record and in the corresponding location of the CRF. After the enrollment of the subjects and at the 1 and 2 months of follow-up, the executive nurse shall receive the corresponding number of drugs at the drug administrator, and the remaining drugs and boxes shall be returned to the drug administrator. If the drug is found or damaged during the preparation process, this box of drugs should not be used, the damaged drugs shall be treated as empty bottles, and other undamaged drugs shall be returned to the drug administrator together with the packaging box. The study center shall be responsible for the management of test drugs, including receiving, distribution, counting and recovery. The investigator shall ensure that the test drug is stored in a safe, independent and locked place at the study site and the storage conditions shall meet the storage requirements of the test drug. No one can be contacted without the consent of the investigator. Empty boxes shall be stored and managed as the test drug.

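### Section 7.1 requires a safety and dose review only when deaths reach 10% of an undefined number of subjects, and Grade 3–4 toxicity never triggers one

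*Protocol*

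**What the plan says.** Section 7.1 sets the trigger: "If the Grade 5 adverse event of CTCAE 5.0 standard reaches 10% of the number of subjects, the study should be discontinued". Despite the verb, what follows is a suspension. Drug safety is then discussed "to determine whether to adjust the dose of drugs in the study protocol, continue the follow-up during the study suspension". The rule counts every Grade 5 event, whatever its cause. It does not say whether its denominator is the planned, enrolled or treated number. Section 5.5.1 plans 19 subjects.

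Other sections collect safety information:

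- The visit schedule in section 5.2.1 has a row for "complication And adverse event assessment", ticked at 9 of the 10 columns after the first. The row for "Liver, kidney, and cardiac function" is ticked at the same 9 and at the first, and heart ultrasound is ticked at 5 of the 10.
- Section 3.2.3 lists LVEF and creatine phosphokinase as safety indicators.
- Section 6.3 adds return visits: "After each medication, the subject should be required to return to the study center for review".
- Section 6.4.1 says of rescues that "the investigator should analyze whether the rescue causes are related to the study".
- Section 8 has every treated patient evaluated for toxicity, with CTCAE grading and a five-level causality rating.

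Section 6.1 gives 20–50 mg bid by body surface area for six 30-day cycles. It has no step for holding, reducing or stopping the dose.

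**The concern.** A suspension rule decides when someone must stop and look at the drug. This one looks only at deaths, and on one reading it waits for the second. Severe non-fatal toxicity would be tested for, graded and analysed case by case, yet it could accumulate to any level without obliging anyone to reconsider the dose.

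The setting adds weight. Section 2.2.3 states a low risk of serious adverse events alongside an approved indication for children "aged 3 years and older with symptomatic, inoperable plexiform neurofibromas (PN"). Section 4.1 enrols adults for whom resection is indicated. The stated reassurance therefore sits beside a population that is not the one being treated.

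This is not detail left to a statistical analysis plan. The heading of section 7.1 asks for the stopping criteria, and the text answers with a specific threshold. The question is whether that threshold is well set.

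**Working it through.** **Inputs.** Trigger: Grade 5 events in at least 10% of subjects (7.1). Planned number: 19 (5.5.1). The documents give no fatal-event rate, so 0.5%, 1%, 2% and 5% per subject are assumptions.

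**1. The planned 19.** The figure reproduces with a one-sample normal approximation at p0 = 0.20, p1 = 0.50, one-sided α = 0.025 and 80% power:

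n = [(1.960·√(0.2·0.8) + 0.842·√(0.5·0.5)) / 0.30]² = 16.13, rounded up to 17. Then 17/0.9 = 18.9, rounded up to 19.

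**2. Deaths needed.**

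- Fixed 19: 0.10 × 19 = 1.9, so 2 deaths. One death is 1/19 = 5.3%; two are 2/19 = 10.5%. Using the 17 evaluable subjects, 1.7 also rounds up to 2.
- Treated to date: 1/10 = 10% triggers; 1/11 = 9.1% does not. From the 11th subject on, two deaths are needed.
- Exact (Clopper–Pearson) 95% interval for the fatal risk: 1/19 gives 0.1% to 26.0%; 2/19 gives 1.3% to 33.1%. One death, which forces nothing on the fixed reading, is compatible with a fatal risk well above 10%.

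**3. How often the rule fires.** With X binomial(19, p):

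- At least one death: 1 − (1−p)^19.
- Fixed-19 rule fires: P(X ≥ 2) = 1 − (1−p)^19 − 19p(1−p)^18.
- Death without a required review, fixed 19: P(X = 1).
- Treated to date, upper bound: P(≥1 in the first 10) + P(0 in the first 10) × P(≥2 in the last 9). This supposes that each outcome is known before the next subject starts. If all 19 have started before the first death, the result falls to the fixed-19 value.

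| Assumed fatal risk | At least one death | Fires, fixed 19 | Death, no required review, fixed 19 | Fires, treated to date (upper bound) |
|---|---|---|---|---|
| 0.5% | 0.091 | 0.004 | 0.087 | 0.050 |
| 1% | 0.174 | 0.015 | 0.159 | 0.099 |
| 2% | 0.319 | 0.055 | 0.264 | 0.194 |
| 5% | 0.623 | 0.245 | 0.377 | 0.444 |

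At 2%, a death without a required review therefore has probability 0.264 on the fixed reading. On the treated-to-date reading it lies between 0.319 − 0.194 = 0.125 and 0.264.

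**4. Grade 3–4 events.** They do not enter the count. Even 19 of 19 subjects with a Grade 3–4 event gives 0 Grade 5 events, and 0% is below 10%. The firing probability is 0 on both readings, with no assumed rate needed.

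**5. Does another section fill the gap?** Sections 5.2.1, 6.3, 6.4.1 and 8 produce tests, visits, grades and case-level causality opinions. None attaches a dose or study-level action to a grade or count. Section 7.2 names dissatisfaction with the effect and cost as reasons for stopping, not toxicity.

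**The case against.** Section 7.1 says when suspension is compulsory and forbids nothing earlier. Section 2.2.3 promises closer attention to subjects, section 8 has the measures taken recorded and events followed up, and section 10 binds the trial to Good Clinical Practice and ethics committee review. This stands. A reader might infer that toxicity goes unwatched or that investigators may not act before the threshold; the documents support neither. What remains is that none of these provisions is a trigger.

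A reader might also infer that a single death can never force a review. That holds only if the denominator is the fixed 19. Counted on subjects treated to date, one death among 10 or fewer does trigger the rule. The Grade 3–4 gap does not depend on this choice.

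The fatal-event probabilities rest on assumed risks spanning a tenfold range. Grade 3–4 toxicity in all 19 shows the rule's logic and is not a forecast: section 2.2.3 describes the most common toxicity as grade 1 and 2.

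Finally, the silence of section 6.1 is an omission. The drug is marketed, its label is not among the documents, and whether label dose modifications would be followed is unknown. That makes it a weaker point than the threshold stated in section 7.1.

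**Conclusion.** The point holds as a badly set rule. The only compulsory study-level review is tied to deaths at 10% of an undefined number. On the planned 19 it needs two deaths; on subjects treated to date, one death suffices only up to the tenth subject. Grade 3–4 toxicity triggers nothing on either reading, and this is the firmest part because it needs no assumption. The fatal-event part depends on the reading and on the assumed risk: a death without a required review has probability 0.087 to 0.377 on the fixed-19 reading for risks of 0.5% to 5%, and can be lower on the other.

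The documents do not show that the dose is unsafe, that severe toxicity is expected or that monitoring is absent. The finding is that the information is collected and no stated rule requires anyone to act on it before the death threshold.

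**What to change.** Amend sections 7.1 and 6.1.

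1. **Deaths (7.1).** Keep the existing all-cause 10% rule and define its denominator as subjects treated to date. Add that any single Grade 5 event not rated *possibly unrelated* or *unrelated* suspends dosing pending a safety and dose review. The all-cause rule must stay: limiting the trigger to related deaths would drop a protection that 7.1 now gives, since two deaths of any cause among 19 already suspend the study. The rating list in section 8 and the definitions beneath it use different labels, so the amendment should say which apply.
2. **Grade 3–4 events (7.1).** Add a study-level review trigger for treatment-related Grade 3–4 events. The sponsor and ethics committee should set the threshold against a stated acceptable rate; the documents give no rate from which to derive one.
3. **Individual dosing (6.1).** Hold dosing at a treatment-related Grade 3 event or if LVEF falls below 50%, the entry limit in section 4.1. After recovery, restart one dose step lower, with the steps listed. Stop permanently if the subject is already at 20 mg bid, at a treatment-related Grade 4 event, or at a repeat Grade 3 event.

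The cost is one amendment resubmitted to the ethics committee, using grades, ratings and tests already collected, and more pauses. At an assumed 2% treatment-related fatal risk, the chance of a suspension for such deaths is 0.319, against 0.055 under the current rule on the fixed-19 reading. Defining the denominator as treated to date also means that one unrelated death among the first 10 subjects would pause the study. Creatine phosphokinase rises without symptoms are listed as common in section 2.2.3, so laboratory-only Grade 3 results may add holds, a burden that cannot be sized from the documents. Each study-level pause is a review, not a termination.

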9.1 Case report form / electronic data records

Prior to the start of the study, the Redcap electronic database / EDC database was established based on the content of the paper version of the case report form.

9.2 Data management (data collection form, data storage carrier: electronic / paper, data integrity inspection, database establishment method, data management system, data quality detection method, definition of data lock library, etc.)

The original data should be uniformly recorded in the study medical records. According to the content of the study medical record, the case report form can be completed in the electronic database to ensure the integrity and accuracy of the information. In order to ensure the accuracy of the data, the researcher shall conduct self-examination no less than twice a year, regularly appoint personnel to the sub-center for project quality control, and accept the examination by the hospital and school management departments. If the data registered in the case report form / electronic database are inconsistent with the original records (study medical records), the investigator shall organize timely verification of the data, modify the wrong part according to the requirements of GCP regulations, and make corresponding explanations if necessary.

10. Ethics requirements

This study complied with the provisions of Good Clinical Practice and the Administration of Investigator-Initiated Clinical Studies (Trial) and the Declaration of Helsinki. This study will be conducted only before the ethical committee of the trial. In the course of the study process, the revised protocol must be resubmitted to the Ethics Committee for review, and the investigator must wait until the consent of the Ethics Committee before implementing the new protocol.

Each enrolled patient must sign an informed consent form. Copies of the informed consent form and contact information of the investigator and the ethics committee must be provided to the requested patients*. This study will collect the clinical data and personal information of the research subjects for scientific research, which will involve the privacy rights of the patients. The study participants and data analysts signed a confidentiality agreement not to disclose patient personal information and disease-related information to any individuals and institutions unrelated to the study. The collected patient data should be managed to prevent personal privacy leakage.

11. References

